Activity / Assessment	Screening / Baseline	Intervention Period (in cycles of 3 weeks)									EoT	Safety Follow up / Discontinuation	Survival Follow-Up / EoS / 1-Year Follow-Up	Notes
	Day -56 to Day -1	Cycle 1 (21 days)		Cycle 2 (21 days)		Cycle 3 and subsequent cycles (21 days)		Within 14 days after decision to withdraw IMP	30 days after the last dose	After Safety Follow-Up, every 3 months, up to 1-year Site Visit or by Telephone				
Cycle Day		1	8	15	1	8	15	1	8	15				
Visit Window		± 3 days			± 3 days			± 3 days				- 3 to + 7 days	± 1 month	
ctDNA sample	X							Cycle 3, 5, 9 and 13 only			X			Collection predose (within 60 min prior to tepotinib dose), before premedication, if applicable (See Appendix 4)
Documentation of RAS/BRAF wild-type status, and high MET amp levels	X													Confirmed prior to enrollment and after disease progression on the previous anti-EGFR therapy by an established test.
Tepotinib until PD or intolerance		QD												Decided by the Sponsor and SMC: Dosing may be stopped at any time to review safety and PK data and allow for adjustments before dosing is resumed. Additional schedules may also be evaluated.
Cetuximab until PD or intolerance		Weekly (Day 1)												See Section 6.1 for details of premedication required prior to first infusion.

Activity / Assessment	Screening / Baseline	Intervention Period (in cycles of 3 weeks)									EoT	Safety Follow up / Discontinuation	Survival Follow-Up / EoS / 1-Year Follow-Up	Notes
	Day -56 to Day -1	Cycle 1 (21 days)		Cycle 2 (21 days)		Cycle 3 and subsequent cycles (21 days)		Within 14 days after decision to withdraw IMP	30 days after the last dose	After Safety Follow-Up, every 3 months, up to 1-year Site Visit or by Telephone				
Cycle Day		1	8	15	1	8	15	1	8	15				
Visit Window		± 3 days		± 3 days		± 3 days			- 3 to + 7 days		± 1 month			
Tumor Assessment (RECIST Version 1.1) based on MRI and/or CT scans and other protocol-defined imaging modalities.	X							X #)					See Section 8.1 Screening tumor assessment needs to happen within 28 days prior to dosing. All evaluations should be documented by the Investigator and images uploaded to the imaging repository, for a possible independent read at a later date. #): C3, C5, C7, C9, C11, C13, C15 and subsequently every 4 cycles until study closure, or disease progression regardless of study intervention modifications/discontinuation. If disease progression is not certain, consider continuing to image.	

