## Follow-up Period

All participants are to be followed up after stop of treatment with tepotinib and cetuximab, including an End of Treatment (EoT) Visit within 14 days of the last dose of tepotinib and/or cetuximab. A Safety Follow-up Visit will occur 30 (- 3 to + 7) days after the last dose of tepotinib and/or cetuximab for all participants who discontinued the study intervention permanently. After the Safety Follow-up Visit, the Survival Follow-up is to be performed every 3 months ( $\pm$ 1 month) at clinic visits or by telephone contact for up to 1 year. Participants' survival information will be collected. Any subsequent anticancer therapy given to the participant until death should be recorded.

Participants who discontinue treatment for reasons other than progressive disease (PD) or death will have additional visits for tumor assessments every 6 weeks until 9 months and every 12 weeks thereafter until disease progression, death, or withdrawal of consent. A  $\pm$  7-day time window is permitted for these additional follow-up visits until 9 months, and  $\pm$  14 days thereafter.

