### 8.1.1 Tumor assessments

Computed tomography/magnetic resonance imaging scans will be performed and collected until disease progression is assessed by the Investigators according to RECIST Version 1.1 or start of new anti-cancer therapy. Radiographic images and physical findings (physical assessments) will be used by the Investigators for the local determination of disease progression and patient's treatment decisions. A Baseline bone scan should be performed in participants known or suspected to have bone metastases at Baseline. At Baseline, tumor lesions will be categorized in target and non-target lesions as described in RECIST Version 1.1. Results for these evaluations will be recorded with as much specificity as possible so that pre- and post-treatment results will provide the best opportunity for evaluating tumor response.

CT or MRI of the chest, abdomen, and pelvis should be conducted to evaluate disease in these locations. Imaging (preferably MRI and including T2/FLAIR) of the head at Baseline for participants who have or are suspected to have central nervous system metastases should be conducted. All lesions in the brain should be considered non-target lesions. Additional anatomic areas should be investigated in case of suspicion of presence of metastases based on signs and symptoms of individual participants. All assessments should be provided by the same physician or radiologist if possible, during the study.

For patients who are enrolled in the study and present with brain metastasis MRI assessments of brain lesions should be performed if possible. When possible, the MRI assessment shall include Coronal 3D Gd-T1WI, Axial TSE/T2WI, Axial FLAIR, Axial T1WI, and Axial Gd-T1WI.

Skeletal lesions identified at Baseline should continue to be imaged at subsequent imaging scheduled visits using localized CT, MRI, or X-ray (using the same method used at Baseline for all visits for any given lesion). After Baseline, whole body bone scans need not be repeated, unless positive at Baseline or clinically indicated.

All protocol-required images should be uploaded to the imaging repository, maintained by or on behalf of an Imaging Research Organization for a potential independent read which may be done at any appropriate time, including at the end of study or later.

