Cytology results will be collected when available. Enlarging pleural/pericardial effusion and/or ascites (fluid collections) may or may not denote progression. The radiologist can utilize cytology findings (if available) to decide if significant new fluid or unequivocal and significant enlarging fluid is an indication of progression.

The Investigator may perform scans in addition to a scheduled study scan for medical reasons or if the Investigator suspects PD. Participants who withdraw from the study for clinical or symptomatic deterioration before objective documentation of PD will be requested to undergo appropriate imaging to confirm PD. Every effort should be made to confirm a clinical diagnosis of PD by imaging according to RECIST Version 1.1.

Participants will be assessed every 6 weeks starting from Cycle 3 Day 1 visit until 9 months, and every 12 weeks thereafter according to RECIST Version 1.1, until disease progression, death, withdrawal of consent, or study closure. Details on how to perform RECIST Version 1.1

assessments are provided in [Appendix 5](#). Investigator assessments will be conducted. Any CR or PR should be confirmed, preferably at the scheduled 6-week interval or at the next scheduled imaging visit, but no sooner than 4 weeks after the initial documentation of CR or PR. In the case of symptoms suggesting progression, participants should be evaluated by imaging thereafter for documentation and confirmation of the tumor responses.

The same method of assessment and the same technique should be used to characterize each identified and reported lesion at Baseline and during the study. If a chest X-ray indicates metastatic disease while the participant is enrolled in this study, a CT of the chest is required for confirmation. All assessments should be provided by the same physician or radiologist if possible during the study.

Participants who withdraw from the treatment for reasons other than progressive disease will have additional visits for tumor assessments every 6 weeks until 9 months, and every 12 weeks thereafter until disease progression. A  $\pm$  7-day time window is permitted for these additional follow-up visits until 9 months, and  $\pm$  14 days thereafter. Reasons for study termination should be recorded if this visit is the last visit for the participant. Recording of any new anticancer therapy will be made (a tumor assessment is mandatory before initiating the new therapy).

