14.2 Secondary Endpoints

14.2.1 Duration of Response

Duration of Response (DoR) as assessed by Investigator will only be evaluated in participants with objective response (as defined in Section 14.1.1).

DoR is the time from when the CR/PR (whichever is first) criteria are first met until PD or death due to any cause within the period of 2 scheduled tumor assessments (84 or 168 days) after the last tumor assessment, whichever occurs first (see Eisenhauer EA, et al 2009) (i.e. date of PD/death - date of last evaluable tumor assessment \leq 84 or 168).

DoR data will be censored on the date of the last evaluable tumor assessment for participants who do not have an event (PD or death) or for participants with an event after the period of 2 scheduled tumor assessment (more than 84 or 168 days) after the last evaluable tumor assessment (i.e. date of PD/death

- date of last evaluable tumor assessment > 84 or 168). Participants who do not have a tumor assessment after objective response will be censored at the date CR/PR criteria are first met.

The last evaluable tumor assessment is defined as the last tumor assessment result that is not “NE”.

Kaplan-Meier estimates (product-limit estimates) will be presented together with a summary of associated statistics for duration of response: median and corresponding two-sided 95% confidence interval (CI), Q1 and Q3, minimum and maximum. DoR rate estimates at 3, 6, 9, 12, 15, 18 months and for every 3 months thereafter as applicable including the corresponding two-sided 95% CIs will also be reported. The CI for the median will be calculated according to Brookmeyer and Crowley (1982) and CIs for the survival function estimates at the above defined time points will be derived using the log-log transformation according to Kalbfleisch and Prentice (1980) (conftype=loglog default option in SAS Proc LIFETEST). The estimate of the standard error will be computed using Greenwood's formula. Kaplan-Meier plots will also be presented.

Time to and duration of response as assessed by Investigator for every participant will be plotted using a swimmer plot. Symbols color coded will be used to show the time of the following events: complete response, partial response, progressive disease, death, ongoing response and end of treatment.

Estimand Attributes

Endpoint:

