14.2.2 Progression Free Survival

Progression Free Survival (PFS) time as assessed by Investigator is defined as the time (in months) from first administration of study intervention to the date of the first documentation of PD or death due to any cause, whichever occurs first if only the event happened within the period of 2 scheduled assessments (84 or 168 days) after the last tumor assessment (i.e. time between date of PD/death - date of last evaluable tumor assessment ≤ 84 or 168 days). The tumor response will be determined according to RECIST 1.1. and assessed by the investigator.

PFS data will be censored on the date of the last evaluable tumor assessment for participants who do not have an event (PD or death) or for participants with an event after the period of 2 scheduled tumor assessments (84 or 168 days) after the last tumor assessment (i.e. date of PD/death - date of last evaluable tumor assessment > 84 or > 168 days).

The last evaluable tumor assessment is defined as the last tumor assessment result that is not “NE”.

Participants who do not have a baseline tumor assessment or who do not have any post baseline tumor assessments will be censored at the date of the start of study intervention.

Participants who do not have an evaluable post-baseline tumor assessment will be censored at the date of the start of study treatment unless death occurred within the period of 2 scheduled tumor assessments (84 or 168 days, respectively) after the first dose of study treatment in which case the death will be considered an event.

The censoring and event date options to be considered for the PFS are presented in [Table 5](#).

Table 4. Date of event / censoring definition for PFS analysis

Status		Censoring	Date of event / censoring
Progressed or died	Within the period of 2 scheduled tumor assessment (84 or 168 days, respectively) after last response assessment of CR, PR or SD or start of treatment	Event	Minimum (Date of PD, Date of death)
	Otherwise	Censored	Date of last tumor assessment with outcome CR, PR or SD or date of start of treatment, whatever is later
Neither progressed nor died		Censored	Date of last tumor assessment with outcome CR, PR or SD or date of start of treatment, whatever is later

CR = Complete Response, PR = Partial Response, SD = Stable Disease, PD = Progressive Disease.

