Kaplan-Meier product-limit estimates will be presented together with a summary of associated statistics for PFS: median and corresponding two-sided 95% confidence interval (CI), Q1 and Q3, minimum and maximum. Progression-free rate estimates at 3, 6, 9, 12, 15, 18 months and for every 3 months thereafter as applicable including the corresponding two-sided 95% CIs will also be reported. The CI for the median will be calculated according to Brookmeyer and Crowley (1982) and CIs for the survival function estimates at the above defined time points will be derived using the log-log transformation according to Kalbfleisch and Prentice (1980) (conftype=loglog default option in SAS Proc LIFETEST). The estimate of the standard error will be computed using Greenwood's formula. Kaplan-Meier plots will also be presented.

Estimand Attributes

Endpoint:

- Progression-free survival time, defined as the time from first dose until PD according to RECIST 1.1 or death events occurring within two scheduled tumor assessments after last evaluable assessment or first dose

Population:

- Participants with *RAS/BRAF* wild-type left-sided metastatic colorectal cancer (mCRC) having acquired resistance to anti-EGFR antibody targeting therapy due to *MET* amplification

Treatment:

- Tepotinib combined with cetuximab

Intercurrent Event Strategy:

- Discontinuation of treatment (treatment-policy strategy, i.e. regardless of the intercurrent event)
- Start of subsequent anti-cancer treatment (treatment-policy strategy, i.e. regardless of the intercurrent event)

- Death within two scheduled tumor assessments after last evaluable assessment will be considered as event of interest (composite strategy)

Population Level Summary:

- Kaplan-Meier estimates

Follow-Up Duration of PFS

In order to assess the follow-up duration of PFS, Kaplan-Meier estimates will be calculated using the censoring rules with the reverse censoring indicator.

Kaplan-Meier estimates (product-limit estimates) will be presented in the same way as in the analysis described above for PFS.

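### PFS and DoR declare treatment policy for subsequent anti-cancer therapy, but the protocol contradicts itself on whether scans continue after it, and no PFS or DoR sensitivity analysis covers the switch

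*SAP*

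**What the plan says.** **Estimand.** The estimand attributes for PFS (SAP 14.2.2) include "Start of subsequent anti-cancer treatment (treatment-policy strategy, i.e. regardless of the intercurrent event". SAP 14.2.1 repeats this for DoR.

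**Censoring.** For DoR, "DoR data will be censored on the date of the last evaluable tumor assessment for participants who do not have an event". For PFS, SAP Table 4 sets the censoring date as "Date of last tumor assessment with outcome CR, PR or SD or date of start of treatment, whatever is later". In both, a progression or death more than 84 or 168 days after the last evaluable scan is censored back to that scan. Neither rule mentions new therapy.

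**Imaging.** The first paragraph of Protocol 8.1.1 collects scans "until disease progression is assessed by the Investigators according to RECIST Version 1.1 or start of new anti-cancer therapy". Three other places give no such stop:
- Protocol 1.3, Schedule of Activities: "until study closure, or disease progression regardless of study intervention modifications/discontinuation".
- Protocol 4.1, Follow-up Period, for participants who stop treatment without progression: "every 12 weeks thereafter until disease progression, death, or withdrawal of consent".
- Protocol 8.1.1, general schedule: "every 12 weeks thereafter according to RECIST Version 1.1, until disease progression, death, withdrawal of consent, or study closure".

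The list of imaging endpoints at the end of 8.1.1 adds a limit tied to the longest permitted duration of treatment. That duration is not defined anywhere.

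**Sensitivity analyses.** SAP 9.8 imputes incomplete start dates of subsequent therapy in order to set censoring dates in efficacy sensitivity analyses. The only sensitivity analysis defined for switching is SAP 14.1.2, for objective response.

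**The concern.** A treatment-policy strategy for a progression endpoint works only if progression is looked for after the participant changes therapy. If imaging stops at the change, the follow-up that the estimand needs does not exist, and the censoring rules decide the result. The protocol supports both readings, so two sites could each follow a protocol sentence and contribute different kinds of data to one Kaplan-Meier curve.

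What is at stake is interpretation. In a single-arm study without tests, readers will set median PFS and DoR against results from elsewhere. They need to know whether those figures follow participants through the next therapy or stop at it.

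**Working it through.** The plan gives no figure on this point and no expected switch rate, so the check is mainly a comparison of passages.

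**1. When does imaging end?**

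| Place | Scans end at | New therapy listed as a stop? |
|---|---|---|
| Protocol 1.3 | study closure, PD | no |
| Protocol 4.1, follow-up | PD, death, withdrawn consent | no |
| Protocol 8.1.1, first paragraph | PD, new therapy | **yes** |
| Protocol 8.1.1, general schedule | PD, death, withdrawn consent, closure | no |
| Protocol 8.1.1, visits after stopping treatment | PD | no; a scan is required before new therapy |
| Protocol 8.1.1, endpoint list | confirmed PD, undefined treatment limit, study end | no |

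The conflict lies partly inside 8.1.1 itself.

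**2. Can a switch without PD happen?** Yes. Protocol 7.1 names the start of other anti-cancer therapy beside PD as a reason to stop study intervention, and 8.1.1 requires a scan before it.

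**3. The SAP rules applied to one invented participant.** SD at the pre-therapy scan on day 100, new therapy on day 101, still SD on day 127, PD visible at C9D1 (8 × 21 + 1 = day 169), death on day 190. Months = days / 30.4375 (SAP 9.5).
- Scans continue: 169 − 127 = 42 ≤ 84, so PFS is an event at 169 / 30.4375 = 5.6 months.
- Scans stop at new therapy: PD is not imaged. Death comes 190 − 100 = 90 days after the last scan, more than 84, so PFS is censored at 100 / 30.4375 = 3.3 months.

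Under the stop rule a death inside the window would count, but a progression on the next therapy never would. The result is a hybrid: neither treatment policy nor a clean cut at the switch.

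**4. Is a sensitivity analysis defined?** SAP 14.1.2 uses the 9.8 date imputation, but for objective response, a yes/no status with no censoring date. SAP 14.2.1 and 14.2.2 contain no analysis that uses the start of subsequent therapy. The reference in 9.8 to censoring dates therefore has no matching time-to-event analysis.

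**5. Illustrative size; every input is assumed.** Simulation of 60,000 participants per scenario: exponential times, median time to PD 4 months, median survival 10 months, death independent of PD and switching. Scans are 6-weekly to day 294, then 12-weekly, with one on the day of the switch. The SAP's 84/168-day rule is applied. The hazard ratio (HR) is for PD after the switch.

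| Switched before PD | HR | 6-month PFS, scans continue | 6-month PFS, scans stop | Gap (points) |
|---|---|---|---|---|
| about 7% | 0.5 | 26.2% | 24.8% | 1.4 |
| about 7% | 1.0 | 25.3% | 24.7% | 0.6 |
| about 8% | 1.5 | 24.9% | 24.8% | 0.1 |
| about 15% | 0.5 | 27.0% | 24.0% | 3.0 |
| about 15% | 1.0 | 25.4% | 23.9% | 1.5 |
| about 15% | 1.5 | 24.2% | 24.0% | 0.2 |
| about 23% | 0.5 | 27.9% | 23.0% | 4.9 |
| about 23% | 1.0 | 25.0% | 22.6% | 2.4 |
| about 24% | 1.5 | 23.5% | 23.0% | 0.5 |

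For scale, an approximate 95% half-width that ignores censoring is 1.96 × √(0.279 × 0.721 / 22) = 0.187 for Cohort A and 1.96 × √(0.279 × 0.721 / 20) = 0.197 for Cohort B. The largest gap, 4.9 points, is about a quarter of either. All participants were put under one rule; a mixture of site practices would be expected to give a smaller gap.

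**The case against.** The best defence is that the protocol, read as a whole, mostly answers the question. New therapy forces withdrawal from study intervention (7.1). Participants who stop without PD are scanned until PD (4.1, 8.1.1). The Schedule of Activities says that discontinuation does not end imaging, and Section 8 calls adherence to that schedule essential. Treatment policy fits these passages. This stands: a reader might infer that the declared estimand cannot be estimated in this trial, and the documents do not support that. The mismatch arises only where a site acts on the one clause in 8.1.1, but nothing tells a site to disregard it.

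Three further inferences also go too far:
- **That PFS and DoR are flawed because they include time on another therapy.** That is what treatment policy means, and the SAP declares it openly.
- **That SAP 9.8 promises an analysis counting the switch as an event.** It speaks of censoring dates, names neither PFS nor DoR, and is already used by 14.1.2. An intended censoring analysis is a fair inference, not a stated plan.
- **That moving one death across day 84 shows the size of the imaging conflict.** That jump comes from the prespecified window and affects anyone whose scans end, for whatever reason.

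There is also some transparency. SAP 12 counts and lists subsequent therapies, and SAP 9.8 flags censored values in listings, so in cohorts of 22 and 20 each switcher can be found. That helps a careful reader but does not show how PFS or DoR would change.

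**Conclusion.** The contradiction is real and should be resolved. One clause of Protocol 8.1.1 stops imaging at new therapy, against the other imaging passages and against the strategy declared for PFS and DoR; a second clause adds an undefined limit. Where the stop is followed, the estimate is a hybrid and not the declared estimand. SAP 14.2 has no sensitivity analysis that would reveal the difference.

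The consequence is limited. Both endpoints are secondary, all analyses are descriptive (Protocol 9.4.1, SAP 9), and no error rate is involved. Only participants who start new therapy before PD are affected; their number is not given and could be zero. The gap of up to about 5 points in 6-month PFS rests wholly on assumed switching, survival and progression rates. It shows an order of magnitude and is not a forecast for this trial. No figure is offered for DoR.

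**What to change.** 1. **Protocol.** Reconcile the first paragraph and the endpoint list of 8.1.1 with 1.3, 4.1 and the rest of 8.1.1 on when imaging ends. Define or delete the limit based on treatment duration.
2. **SAP 14.2.1 and 14.2.2, estimand.** Make the strategy follow the reconciled rule. If scans continue after new therapy, keep treatment policy. If they do not, restate the strategy as assessments up to new therapy, as the SAP already does for objective response, with censoring to match and a statement on deaths after the switch.
3. **SAP 14.2.1 and 14.2.2, sensitivity.** Add a descriptive analysis that censors at the last evaluable scan before the start of subsequent anti-cancer therapy. Use the 9.8 date imputation and the 14.1.1 rule that a scan on the start day counts as before therapy. Say in the report that it assumes switching is unrelated to prognosis. Counting the switch as an event may be added as a separate supplementary analysis, but should not be presented as the one to which 9.8 refers.

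The cost is one protocol clarification, some SAP wording and a few descriptive tables from dates already collected.
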